Table 11: ADEs – Time of Occurrence and Outcome

Adverse Device Defect	Total (N=13)												Outcome
	First 4 weeks			First 16 weeks			First 28 weeks			First 12 months			
	n	%	AE	n	%	AE	n	%	AE	n	%	AE	
Any System Organ Class	1	7.7	3	3	23.1	8	4	30.8	11	4	30.8	15	
Eye Disorders	2	15.4	2	4	30.8	6	4	30.8	9	4	30.8	13	
Cystoid macular edema	0	0.0	0	2	15.4	3	3	23.1	4	3	23.1	6	4 recovered 1 recovering 1 recurrent
Hypotony of eye	0	0.0	0	0	0.0	0	1	7.7	1	2	15.4	2	recovered
Anterior chamber cell	1	7.7	1	1	7.7	1	1	7.7	1	1	7.7	1	recovered
Iris adhesion	0	0.0	0	1	7.7	1	1	7.7	2	1	7.7	2	recovered
Pigment dispersion	1	7.7	1	1	7.7	1	1	7.7	1	1	7.7	1	recovered
Vitritis	0	0.0	0	0	0.0	0	0	0.0	0	1	7.7	1	recovered
Investigations	1	7.7	1	1	7.7	1	1	7.7	1	1	7.7	1	
Intraocular pressure increased	1	7.7	1	1	7.7	1	1	7.7	1	1	7.7	1	recovered
Product Issue	0	0.0	0	1	7.7	1	1	7.7	1	1	7.7	1	
Retroprosthetic membrane	0	0.0	0	1	7.7	1	1	7.7	1	1	7.7	1	not recovered

Source: Final Statistical Output – Tables

Table 14.3.1.6 – Adverse Device Effects by SOC and PT – periods first 4 weeks, 16 weeks, 28 weeks, 12 months following implantation surgery

#: Percentage based on N

N: Number of subjects in total (Safety Set)

n: Number of patients reporting at least one adverse event with the specification

AE: Number of individual adverse events which occurred among the n patients

 Implantata Ophthalmic Products GmbH	Clinical Investigation Report ARGOS-KP01	Revision A Page 86 of 114
--	---	----------------------------------

Of the 15 ADEs, three were classified as mild, six as moderate and six as severe.

- Anterior chamber cell: moderate
 - Inflammation is a normal and common response to any trauma of the eye, including intraocular surgery. A moderate intraocular inflammation after surgery is expected and can be caused by the implantation of the Boston keratoprosthesis as well as by the manipulation of the iris caused by the implantation of the ARGOS-IO sensor. A self-resolving, sterile anterior chamber inflammation after surgery is not expected to negatively impact device functioning, healing or functional recovery.
- Cystoid macular edema: 3 moderate, 3 severe
 - A cystoid macular edema is a known complication of all intraocular surgeries and has in most times a self-limiting nature. In stand-alone BK-Pro surgery, CME is with up to 27% also a frequent complication (Moshin H. Ali, 2018). However, a causal relationship with the ARGOS-IO sensor can never be excluded.
- Hypotony of eye: 1 moderate, 1 severe
 - Boston keratoprosthesis represents a second line surgical treatment in eyes, where primary keratoplasty has a low chance of success. In many cases, eyes scheduled for keratoprosthesis surgery experienced ocular trauma or condition after multiple surgical interventions. Due to a lack of aqueous humor production and/or leakage because of insufficient corneal sutures, hypotony of the eye is an expected event after surgery. Therefore it is unlikely, that the device itself caused hypotony of the eye.
- Iris adhesion: severe
 - Iris adhesions can occur between the iris and the sensor and as anterior synechiae between iris and cornea. Both phenomena can be caused as a consequence of Boston keratoprosthesis surgery. The additional volume in the posterior chamber related to the ARGOS sensor might have an impact on formation of adhesions. However, as this ADE only occurred in one case, the significance may be questioned.

 Implantata Ophthalmic Products GmbH	Clinical Investigation Report ARGOS-KP01	Revision A Page 87 of 114
--	---	----------------------------------

- Pigment dispersion: *mild*
 - Manipulation of the iris may lead to disruption of cells of the pigmented layer of the iris and dispersion of pigment granula into the anterior chamber. The pigment can settle anywhere in the anterior chamber, frequently showing as non-symptomatic small deposits on the posterior surface of the cornea or anterior surface of the IOL. This is not limited to the implantation of the ARGOS-IO sensor but to any anterior chamber surgery during which there is accidental or initial manipulation the iris. A second potential cause of pigment release after initial surgery can be posterior iris chafing on the sensor placed in the ciliary sulcus.
- Vitritis: *moderate*
 - Vitritis in the posterior chamber is the equivalent intraocular inflammation in the anterior chamber. A moderate vitritis after surgery is expected with a frequency of up to 23% in stand-alone BK-Pro of aniridia patients (Salima I. Hassanaly, 2014) and can be caused by the implantation of the Boston keratoprosthesis as well as by manipulation of caused by the implantation of the ARGOS-IO sensor. A self-resolving, sterile posterior chamber inflammation after surgery is not expected to negatively impact device functioning, healing or functional recovery.
- Intraocular pressure increased: *mild*
 - A postoperative increase in intraocular pressure can be considered as an expected event, not only in this study, but highly frequently after intraocular surgery.
- Retroprosthetic membrane: *moderate*
 - Formation of a retroprosthetic membrane is a key adverse event after stand-alone Boston keratoprosthesis surgery and represents with >50% the most frequent complication after BKPro surgery (Lee WB, 2015). Therefore, the occurrence in this study is not surprising. An additional impact of the ARGOS sensor on formation of the membrane cannot be fully ruled out excluded. But giving the extent and the frequency of membrane formation after stand-alone keratoprosthesis surgery, it seems more likely to be caused by the procedure itself.

 Implantata Ophthalmic Products GmbH	Clinical Investigation Report ARGOS-KP01	Revision A Page 88 of 114
--	---	----------------------------------

To summarize, all potential ADE's can be caused by the stand-alone procedure and they are not of a higher percentage in this study than in other known publications. The overall benefit to offer IOP measurement in a situation where - without implantable device - only palpitory IOP would be possible outweighs a possibly increased likelihood of occurrence of theses ADE's.

4.8.2 Concomitant Medications

No restrictions were placed on patients' use of concomitant medications during study participation.

Antiglaucoma preparations and miotics were used in 12 patients.

4.8.4 Examination Results over Time

All relevant and clinical significant findings of the anterior and posterior segment following surgery were documented as adverse events.

4.8.4.1 Visual Acuity

Visual acuity was measured using the Early Treatment Diabetic Retinopathy Study (ETDRS) protocol. There was no measurement scheduled for the baseline visit but for Visit 07 (4 weeks post surgery) and V15 (52 weeks post surgery). The mean number of letters correctly read by 12 patients at V07 was 1.7 (SD 2.7) (range 0-9). For V15, the visual acuity was measured in 7 patients. The mean number of letters correctly read was 7.7 (SD 13.8) (range 0-34).

 Implantata Ophthalmic Products GmbH	Clinical Investigation Report ARGOS-KP01	Revision A Page 98 of 114
--	---	----------------------------------

5 DISCUSSION

5.1 Limitations of the Study

Several aspects of the study limited its conclusiveness.

1. Only 12 patients were included and only 9 patients finished the study, which is sufficient to detect problematic design features that lead to common adverse events and still limits the number of patients that could potentially be harmed due to unforeseen events. However, with this low number of patients it is unlikely to detect rare negative effects particularly with regard to the different underlying diseases of these patients and different indications for the Boston-Keratoprosthesis implantation.
2. 12 months follow-up for a device intended for permanent implantation are too short to detect any long-term complications or late device deficiencies in patients with Boston Keraprosthetic. Since the device itself is technical identical to the CE approved EYEMATE-IO device, to be placed into the posterior chamber/ciliary sulcus of the eye during cataract surgery and this device performs well for more than several years, no main device related issues are to be expected.
3. Although surgical manometry is the only available method to accurately measure IOP in BKPro patients, it carries problems in the performance and therefore some limitations for the comparability with ARGOS-IO measurements:
 - a. Due to the puncture of the bulbus and following removal of the needle, aqueous humor can be lost which lead to a decrease of the intraocular pressure.
 - b. The quality of the measurements can be strongly influenced by experience of the investigator.

5.2 Safety and Tolerability

The overall outcome of the ARGOS-KP01 clinical trial provide sufficient evidence that the ARGOS-IO system is safe and well tolerated in to support its implantation in patients with an indication for a BKPro. Adverse events and serious adverse events in this study were in line with the expected complications after BKPro surgery (Lee WB S. R., 2015) (Ahmad S M. P., 2016). Most frequent complications were formation of a retroprosthetic membrane and hypertonic or hypotonic IOP. The study investigators saw the causality of most adverse events linked to the implantation of both the BKPro and the ARGOS-IO sensor. While it is not possible to clearly differentiate causality between

 Implantata Ophthalmic Products GmbH	Clinical Investigation Report ARGOS-KP01	Revision A Page 99 of 114
--	---	----------------------------------

those two potential causes, all observed complications are also well known to occur in stand-alone BKPro implantation.

5.3 Performance

Performance data acquired in this study showed overall good consistency between manometric and telemetric IOP results and between ARGOS-IO and finger palpation. There was not seen a trend for increasing discrepancies between modalities during the follow-up.

The technical performance of the components of the ARGOS-IO system during the ARGOS-KP01 trial was good. There were no major device deficiencies of any of its components that compromised the safety of the patients in the trial. None of the adverse events reported for the trial where a direct or indirect result of a device deficiency.

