As a result of these tests and the ARGOS-01 study, modifications were made to the form of the device and the implantation procedure to improve the device's safety profile. The implant thickness was reduced from 0.9 mm to 0.5 mm overall, tapering to a rounded outer edge of only 0.1 mm, and haptics were added to the device to better maintain its positional stability and to reduce mechanical stresses of the sensor on the eye. In addition, four haptic arms and two allantoid protrusions on the posterior surface of the ring were added to the ring to improve its positional stability, facilitate unfolding and better distribute pressure on the ring. When subjected to radial force, the redesigned sensor ring did not show the abnormalities in pressure readings or the plane distortions seen in the earlier version. The implant is also now available in three different diameters to allow selection of the implant size that best fits the individual participant. Related procedural changes, including the use of a cartridge injector similar to those used to insert foldable IOLs to insert the implant and first use of the sensor at 30 days post-surgery instead of at day 1 to 3 as in the previous study, are expected to reduce potential stress to the patients' anterior chambers during surgery and the initial post-surgical period. Together, these changes are expected to reduce irritation of the iris and pressure drifting observed in the ARGOS-01 study.

Due to the unique form of the human eye, and the exacting nature of the fit, it is not possible to assess the effects of the design modification in animals.

In May 2017, the ARGOS-IO system got the CE approval as intraocular pressure sensor for measurement of intraocular pressure in patients with primary open angle glaucoma due to the ARGOS-02 study. This clinical trial investigated the safety and performance of the ARGOS-IO systems in patients with primary open angle glaucoma undergoing phacoemulsification and IOL implantation for cataract and received ARGOS-IO implants in an add-on procedure. 22 patients were enrolled and their eye condition and IOP were followed over a course of 12 months. The ARGOS-IO measurements showed an excellent level of concordance to the conventional Goldmann Applanation tonometry and no device related serious adverse events were recorded (Implantata, 2017).

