One objective of this study was to verify the device's accuracy in the patient population. Patients will benefit from a continual long-term monitoring of IOP independent from visits to the ophthalmologist. The Sponsor plans to develop an internet platform that will permit the physician to remotely access information from individual readings, allowing patients' IOP to be monitored by the treating physician between office visits. This will permit a more rapid response to changes in IOP and a better fine-tuning of treatment protocols.

Because of the high risk of critically IOP values possible in BKPro patients, glaucoma may progress more rapidly as at open angle glaucoma patients, which requires an even closer monitoring regimen. An additional effect may be improved adherence to prescribed treatment regimens. The potential consequences of poor IOP control are serious and can lead to irreversible loss of vision and accompanying handicap. Patient self-measurement is expected to motivate better compliance with the treatment regimen, thereby facilitating improved IOP control and optimizing long-term outcome.

The ARGOS-KP01 clinical trial was conducted to address these questions:

Compatibility with Boston-Keratoprosthesis

The ARGOS-KP01 study confirmed that it possible to implant a BKPro and ARGOS-IO sensor without mutual interference.

Irritation, Inflammation of Eye, Iris Pigment Abrasion

Does the implant cause irritation, inflammation and pigment abrasion?

 Implantdata Ophthalmic Products GmbH	Clinical Investigation Report ARGOS-KP01	Revision A Page 101 of 114
---	---	-----------------------------------

- Implant surface material has history as IOL material for ocular implantation, with well-known biocompatibility properties; material surface is soft, edges are rounded and smooth, possible small material flashes are soft and atraumatic
- In ARGOS-KP01 trial, the ARGOS-IO device was found to be safe and well tolerated within the eye. No higher levels of irritation, inflammation and pigment abrasion were observed compared to standard Boston Keratoprosthesis implantation and were manageable under standard of care.

Accuracy, precision and sensor drift

Does the ARGOS-IO device exhibit acceptable levels of accuracy and precision?

- Accuracy, precision and sensor drift have been tested and validated in bench tests and in animal trials

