- The ARGOS-IO device was compared to finger palpation (the current gold standard in BI-KPro patients) within this clinical trial and showed a positive statistically significant difference of telemetric IOP measurements between the finger palpation categories (soft hypertonic, normal, borderline, hypertonic).
- ARGOS-KP01 trial has shown that the human anatomy does not have an impact on the accuracy of the device. It is recommended to re-calibrate the device once a year and following ocular surgery.

Usability

The patient acceptance of the ARGOS-IO system at home was very good, showing a very high overall acceptance in using the ARGOS-IO system in their daily routine. The instruction for use for the Mesograph reader device was easily to understand, the implant did not cause them any problems and the patients were less concerned about unidentified high IOP.

Compatibility of the ARGOS-IO implant with Glaucoma drainage devices (GDD)

Compatibility of the ARGOS-IO implant with Glaucoma drainage devices (GDD) was an issue that was long discussed within the risk analysis team. This clinical trial showed if the GDD is placed in the anterior chamber, there is no physical contact with the ARGOS-IO implant, which is located in the ciliary sulcus, and consequently no interference occurs between the two devices.

 Implantdata Ophthalmic Products GmbH	Clinical Investigation Report ARGOS-KP01	Revision A Page 102 of 114
---	---	-----------------------------------

Overall Summary: Based on the clinical study results, risk management effort and user information, it is concluded that the benefits for a patient from the implantation of an ARGOS-IO implant device outweighs the risk. Predicate implantable ophthalmic medical devices, like Boston-Keratoprosthesis, show that there is also residual risk with regard to the surgical procedure in general. The adverse event rate by combining BKPro implantation with EYEMATE-IO/KP insertion is similar to BKPro implantation alone and adverse events were in general manageable under standard of care. **The medical benefit of the implantation of the device, and resulting possibility of direct IOP measurement and frequent self-tonometry by the patients at home clearly outweighs the identified residual risks of the device. The residual risks and their probability of occurrence are within the acceptable range, compared to similar marketed devices in the ophthalmic field.**

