8.3. Rescue Medication

N/A

9. Performance Analyses

All statistical tables will show the results for all patients of the PPS (primary analyses) and the SFS.

Concerning IOP, a summary of all manometry and ARGOS-IO system measurements will be displayed in a table by visit (Week 4, 16, 28, 52 visit): For each patient the mean value of the ARGOS-IO system measurements (mean within subject value) at the visit will be derived and the difference to the manometry value calculated.

The difference between manometry and ARGOS-IOP measurements will be displayed over time in a mean value plot.

Pairs of measurement will only be used when there was no more than 2 minutes difference between manometry and ARGOS-IO system measurements.

All measurement values including the mean within subject ARGOS IOP value will be displayed in a patient data listing. In addition, the time points of measurements and the difference between the time points will be presented in the listing.

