9.1. Primary Performance Endpoint

Primary performance endpoint is the level of agreement between IOP measurements made using manometry and the ARGOS-IO system over the first 12 months following implantation of the IMD.

A Bland-Altman analysis will be done for a point estimation of the level of agreement between the two IOP measurement methods with repeated observations. It is assumed that the true IOP value varies over time for each patient.

Concerning ARGOS-IO, the average of the (three) measurements during surgical manometry will be taken.

All complete measurement pairs (manometry value, average of the ARGOS-IO values during surgical manometry) will be used per patient, to calculate the mean within subject difference between the methods. Pairs of measurement will only be used when there was no more than 2 minutes difference between both measurements.

The average over the mean within subject differences (Δ) is an estimate for the bias between the two IOP measurement methods. The lower and the upper level of agreement will be estimated as

$$\text{LoA}_{\text{low}} = \Delta - z_{\beta/2} * s$$

$$\text{LoA}_{\text{upp}} = \Delta + z_{\beta/2} * s$$

($z_{\beta/2}$ is the upper $\beta/2$ quantile of the standard normal distribution ($=1.96$), s is an estimate for the variation of the differences which comprises both between and within individual components, see Zou, section 2.1.1)

95% confidence interval estimation for the lower limit of agreement (LoA_{low}) and for the upper limit of agreement (LoA_{upp}) will be obtained using the MOVER method, see Zou, section 2.2.2.

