9.2. Secondary Performance Endpoint: Level of Agreement at Specific Visits

Secondary performance endpoint is the level of agreement between IOP measurements made using surgical manometry and the ARGOS-IO system at visits 4, 16, 28 and 52 weeks following implantation.

For each of the visits mentioned above a Bland-Altman analysis will be done to assess the level of agreement between the two IOP measurement methods. Concerning ARGOS-IO, the average of the (three) measurements during surgical manometry will be taken.

For each of the visits mentioned above, the mean of the within subject differences and 95% limits of agreement between the two methods will be calculated. Pairs of measurement will only be used when there was no more than 2 minutes difference between both measurements.

For each of the visits mentioned above, the within subject differences will be plotted against the within subject means (Bland-Altman plot).

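### The statement that no trend was seen is descriptive: the plan estimates no within-patient drift with a confidence interval, so drift is not bounded

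*Protocol*

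**What the plan says.** **The conclusion.** Protocol 5.3 states: "There was not seen a trend for increasing discrepancies between modalities during the follow-up". That section gives no slope, interval or number of patients.

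**Why drift is on the table.** Protocol 1.3 says of the redesign that "these changes are expected to reduce irritation of the iris and pressure drifting observed in the ARGOS-01 study". Among the questions the trial was conducted to address, Protocol 5.5 has one headed "Accuracy, precision and sensor drift". The question worded under that heading asks only about accuracy and precision, and drift is answered with "Accuracy, precision and sensor drift have been tested and validated in bench tests and in animal trials". The same section adds: "It is recommended to re-calibrate the device once a year and following ocular surgery".

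**What is planned.**
- SAP 9: "The difference between manometry and ARGOS-IOP measurements will be displayed over time in a mean value plot".
- SAP 9.1: the average of the patient mean differences "is an estimate for the bias between the two IOP measurement methods". It is a single value over all visits, with limits of agreement and MOVER intervals for those limits.
- SAP 9.2: at each of weeks 4, 16, 28 and 52, "the mean of the within subject differences and 95% limits of agreement between the two methods will be calculated", with a plot of difference against mean.
- SAP 5.2 excludes covariates, 5.3 rules out imputation, and 5.6 plans descriptive analyses with 95% intervals and no tests.
- Protocol 3.6 adds time plots of individual values. The list of figures has nine single-patient plots of the difference over time (Figures 8 to 16), one for all patients (Figure 17), and Bland-Altman plots by visit and overall (Figures 18 and 19).

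**The concern.** The device is meant to stay in the eye permanently, and an earlier design drifted. For such a sensor the useful clinical result is how much the error could have changed over the year. The plan has no parameter for this. SAP 9.1 averages over time. SAP 9.2 gives four separate means, states no interval for them and makes no contrast between them. The plots leave the judgement to the eye, with at most four manometry points per patient.

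Failing to see a trend in so few data is not evidence that drift is small. A reader of Protocol 5.3 could take the statement as support for stable readings over 12 months, and the data may or may not provide that support. Protocol 3.6 also foresees an eventual correction factor. If that factor were a constant, it would be right only if the error depended on neither time nor pressure level, and the plan estimates neither dependence.

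**Working it through.** The documents give no drift estimate, drift margin or SD of the paired difference, so there is no planned figure to reproduce. The only constant in the SAP 9.1 limits, 1.96, is correct. All SDs below are assumptions.

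**1. What a slope estimate could exclude**
- Manometry at weeks 4, 16, 28 and 52 (Protocol 3.3.2): mean week 25, sum of squares 21² + 9² + 3² + 27² = 1260 per patient.
- Patients who finished: 9 (Protocol 5.1). With patient intercepts and a common slope, df = 36 − 9 − 1 = 26 and t = 2.056.
- 95% half-width per year = 52 × t × SD / √(9 × 1260) = 52 × 2.056 × SD / 106.5 = 1.004 × SD.

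| Assumed within-patient SD (mmHg) | Half-width (mmHg per year) |
|---|---|
| 1.5 | 1.5 |
| 2 | 2.0 |
| 3 | 3.0 |

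The normal quantile in place of t gives 1.4, 1.9 and 2.9, slightly too narrow.

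**2. How incomplete data widen this (SD 2)**
- Six complete patients (17 df, t = 2.110): 52 × 2.110 × 2 / √(6 × 1260) = 2.5 mmHg per year.
- Nine patients with weeks 4, 16 and 28 only (sum of squares 288, 17 df): 52 × 2.110 × 2 / √(9 × 288) = 4.3 mmHg per year.
- Nine patients whose true drifts differ with SD 2 mmHg over 48 weeks (random slope, 8 df, t = 2.306): 2.306 × √((48² × 4 / 1260 + 4) / 9) = 2.6 mmHg over 48 weeks, or 2.6 × 52/48 = 2.8 per year.

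**3. What the pooled bias does with real drift**
Suppose a linear drift of 4 mmHg from week 4 to week 52. The errors at the four visits are 0, 1, 2 and 4.
- Pooled bias = 7/4 = 1.75 mmHg, which is 2.25 short of the week-52 error.
- With SD 2, the limits' half-width goes from 1.96 × 2 = 3.92 to about 1.96 × √(4 + 2.92) = 5.15 mmHg, where 2.92 is the variance of the four errors. Drift appears only as wider limits, not as drift.

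The by-visit means of SAP 9.2 would show this pattern, but with no interval on the change.

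**4. Changing patient set**
If 12 patients become 9, and the mean offset of the three lost lies d away from that of the rest, the visit mean moves by d × 3/12: 0.5, 1.0 or 2.0 mmHg for an assumed d of 2, 4 or 8. Protocol 4.5 ties missed manometries to hypotony and to one site stopping the procedure in aniridia patients after SAEs, so random loss cannot be assumed.

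**5. Why level dependence needs care**
Regressing the difference on the pair mean gives a slope even with no true dependence when the two error variances differ: slope = ½(σ²_man − σ²_ARGOS) / (σ²_IOP + ¼(σ²_man + σ²_ARGOS)). Assume error SD 2 for manometry, 0.67 per ARGOS reading averaged over three (variance 0.67²/3 = 0.15), and true-IOP SD 6. The slope is then 1.925 / 37.04 = 0.05, or about 0.5 mmHg per 10 mmHg, with nothing real behind it.

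**The case against.** The plan contains more than a mean plot and a constant bias. Visit-specific bias and limits are estimated, difference-against-mean plots are planned at each visit, and the single-patient difference plots cannot be distorted by a changing patient set. A reader might infer that drift and level dependence are ignored altogether. They are displayed, and that inference fails.

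The changing-set argument is also limited. The primary performance analysis uses the per-protocol set, whose definition (SAP 4.1) requires the full data set to week 28. Apart from pairs lost to the 2-minute rule, weeks 4, 16 and 28 should come from essentially the same patients. The effect in step 4 bears mainly on week 52 and on the safety-set analysis.

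Drift is not an objective or endpoint, the study is described as exploratory, and the drift in Protocol 1.3 concerns an earlier design. The re-calibration advice does not show that drift occurred. The 2 mmHg sensor accuracy in Protocol 2.2.1.1 is a 3-sigma specification and not a drift margin; at an assumed SD of 1.5, a half-width of 1.5 around zero would exclude 2 mmHg per year. The counts of hypotony (6 of 13) and raised IOP (8 of 13) are adverse events and do not describe the range of the paired readings.

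A reader might also infer that drift was never estimated anywhere. Much of the tonometry results text and the figures were not available for this review. Protocol 5.5 reports a statistically significant palpation result although the SAP planned no tests, so unplanned analyses did occur. The gap can be asserted for the plan only.

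All of this stands. What remains is that the planned analyses show data and visit means but put no interval on change within patients.

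**Conclusion.** The point holds in a limited form. The plan has no within-patient slope over time, no confidence interval on the change in bias, and no regression of the difference on pressure level. SAP 9.2 states no interval for the visit means, and the general commitment in SAP 5.1 covers the limits of agreement only. The sentence in Protocol 5.3 is therefore an observation and does not bound drift.

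For size: a zero estimated slope would leave drift of about 1.5 to 3.0 mmHg per year unexcluded for assumed SDs of 1.5 to 3, given nine patients complete at all four visits and a common slope. Both conditions are favourable, and the half-width scales directly with the unknown SD.

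This does not show that the sensor drifted or that the conclusion is false. The documents support only that its uncertainty is not quantified in the plan. It is worth correcting because the repair is cheap and the device is permanent.

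**What to change.** - Add to SAP 9.1 a supportive mixed model of the manometry–ARGOS pair difference on weeks since implantation, with a patient random intercept and, if estimable, a random slope as a sensitivity analysis. Label it post hoc if it is run after the final outputs (21 February 2018).
- Report drift in mmHg per year with a t-based 95% CI, the number of patients per visit, and an analysis restricted to the same patients throughout.
- Add 95% CIs to the by-visit bias in SAP 9.2.
- Report level dependence only as exploratory, with the caveat that regression on the pair mean is biased when the two methods have unequal error variance.
- State whether any sensor was re-calibrated to manometry during follow-up. Protocol 3.3.1 says the manometry readings served to verify or calibrate the sensor, and re-calibration could mask drift in any of these analyses.
- Reword Protocol 5.3 along the lines of: no trend was visible; estimated drift X (95% CI) mmHg per year.

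The cost is one extra model on existing pairs. The interval will be wide and the conclusion will read less favourably.
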